10.1.1.2 Time at risk (days)

Definitions for time at risk (days) are provided as follows:

- For participants who complete the Week 16 visit and continue to the Maintenance Treatment Period:
 - Date of first dose in the Maintenance Treatment Period – Date of first dose in the Initial Period + 1.
- For participants who discontinue on or prior to the final visit of the Initial Period, use the minimum of the following:
 - Date of last dose in the Initial Treatment Period – Date of first dose in the Initial Treatment Period + 141
 - The total number of days in the Initial Treatment Period (112 days). For AEs that emerged after 112 days but still within the 140 days window, those AEs would be

classified as TEAE, but will be excluded from the output based on the Initial Treatment Period. However, these AEs will be included in the AE summaries for Maintenance Treatment Period.

- Date of last clinical contact – Date of first dose in the Initial Treatment Period + 1.
- For participants who die prior to the final visit of the Initial Treatment Period: Date of death – date of first dose in the Initial Period +1.

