3.5.5 Active Medication Set

The Active Medication Set (AMS) will consist of all participants who have received at least 1 dose (full or partial) of bimekizumab. The AMS will be used for summaries of safety that include all data from the Initial Treatment Period and/or Maintenance Treatment Period.

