3.5.6 Maintenance Set

The Maintenance Set (MS) will consist of all participants who have received at least 1 dose (full or partial) of bimekizumab in the Maintenance Treatment Period.

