10.2.1 Data considerations

Treatment-emergent AEs are defined as those AEs that have a start date on or following the first dose of study treatment through the final dose of study treatment + 140 days (covering the 20-week SFU period). If it is not possible (due to partial dates) to determine whether or not an AE is treatment-emergent then it will be assumed to be a TEAE.

An AE will be assigned to the Initial Treatment Period if it started between the first administration of IMP on Day 1 up to Week 16. An AE will be assigned to the Maintenance Treatment Period if it started between the Week 16 study drug administration and Week 48.

If an AE occurs on the date of a treatment switch, the event is attributed to the original treatment. The only exception to this is if the AE fulfills any of the criteria specified below:

- Events that fulfill the anaphylaxis criteria for acute events (refer to Appendix A in Section 12.1)
- Hypersensitivity events identified by the SMQ “Hypersensitivity (SMQ)” (see Section 12.1 Appendix A)
- Events with an high level term (HLT) of “Administration site reactions NEC”
- Events with an HLT of “Injection site reactions”

The rules for imputing partial start or stop dates are outlined in Section 4.2.4.

Any TEAEs that occur during the SFU Period will be attributed to the period in which the participant was before initiating the SFU Period.

Duration of AEs will not be calculated if there is missing stop date information.

If the intensity of an AE is unknown, it is considered as severe. If the relationship to study drug is missing, it is considered as related. Note that if the seriousness of an adverse event is unknown, every attempt should be made to resolve this prior to a snapshot for an interim analysis or database lock; in the exceptional case that the seriousness of an adverse event is still missing then no imputation should be applied for this characteristic.

Adverse events will be presented as “number of participants (percentage of participants) [number of events]”. In this style of output, “[number of events]” will include all cases of an AE including repeat occurrences in individual participants, while “number of participants” will count each participant only once.

Subject time at risk represents the time a participant is at risk for having an AE. The definitions for subject time at risk (in days) are outlined in Section 10.1. These definitions will be used for exposure-adjusted AE summaries.

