10.2.2 AE summaries

The following summaries will be provided by treatment group for the Initial Treatment Period, and the Initial and Maintenance Treatment Period combined based on the SS, and AMS respectively. In addition, all summaries of TEAEs based on “100 subject years” will include EAIR (with 95% confidence interval) and EAER. For AEs that emerged after 112 days but still within the 140 days window, those AEs would be classified as TEAE. These AEs will be excluded from the outputs based on the Initial Period but included in the AE summaries for Initial and Maintenance Treatment Period.

- Incidence of TEAEs – Overview
- Incidence of TEAEs per 100 subject years by SOC, HLT, and PT
- Incidence of Serious TEAEs per 100 subject years by SOC, HLT, and PT
- Incidence of TEAEs Leading to Study Participant Discontinuation per 100 subject years by SOC, HLT, and PT
- Incidence of TEAEs Leading to Death by SOC, HLT, and PT
- Incidence of TEAEs by Maximum Relationship by SOC, HLT, and PT
- Incidence of Serious TEAEs by Relationship SOC, HLT, and PT – Note: For EudraCT reporting purposes
- Incidence of Related Serious TEAE by SOC, HLT, and PT
- Incidence of Severe TEAE per 100 subject years by SOC, HLT, and PT

- Incidence of TEAEs Leading to Death by Relationship by SOC, HLT, and PT – Note: For EudraCT reporting purposes
- Incidence of TEAEs by Maximum Severity, SOC, HLT, and PT
- Incidence of TEAEs by decreasing frequency of PT
- Incidence of TEAEs Above Reporting Threshold of 5% by SOC and PT
- Incidence of Non-Serious TEAEs by SOC, HLT, and PT
- Incidence of Non-Serious TEAEs by Maximum Relationship SOC, HLT, and PT
- Incidence of Non-Serious TEAEs Above Reporting Threshold of 5% by SOC and PT
- Incidence of Non-Serious TEAEs Above Reporting Threshold of 5% by Relationship SOC and PT
- Incidence of Related TEAEs per 100 subject years by SOC, HLT, and PT
- Incidence of Related TEAEs Above Reporting Threshold of 5% by SOC and PT
- Incidence of TEAEs – Suspected and Confirmed COVID-19 cases by SOC, HLT and PT
- Incidence of TEAEs Excluding TEAEs Exclusively Related to COVID-19 Vaccine by SOC, HLT, and PT
- Incidence of TEAEs Exclusively Related to COVID-19 Vaccine by SOC, HLT, and PT
- Incidence of COVID-19 Vaccine Interval Censored TEAEs by SOC, HLT, and PT
- Incidence of COVID-19 Vaccine Interval TEAEs by SOC, HLT, and PT

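### For participants who stop in the Initial Period, the SAP sends TEAEs after Day 112 to inconsistent destinations, and late TEAEs of never-bimekizumab placebo participants reach no TEAE summary table

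*SAP*

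**What the plan says.** Section 10.2.1 makes an AE treatment-emergent if it starts between the first dose and 140 days after the last. The SAP then places TEAEs after Day 112, for participants who stop in the Initial Period, in three ways.

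- **10.1.1.2 (Initial Period time at risk).** The events are "classified as TEAE, but will be excluded from the output based on the Initial Treatment Period". The section continues: "However, these AEs will be included in the AE summaries for Maintenance Treatment Period".
- **10.2.2 (AE summaries).** The events are likewise kept out of Initial Period output, "but included in the AE summaries for Initial and Maintenance Treatment Period".
- **10.2.1 (data considerations).** "Any TEAEs that occur during the SFU Period will be attributed to the period in which the participant was before initiating the SFU Period". For someone who stopped before Week 16, that earlier period is the Initial Period. The same section assigns an AE to the Initial Period only if it started by Week 16.

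The analysis sets decide what each rule can deliver. Section 10.2.2 builds the Initial Period tables on the Safety Set, the combined tables on the Active Medication Set (AMS) and the Maintenance tables on the Maintenance Set (MS). The MS requires participants to have "received at least 1 dose (full or partial) of bimekizumab in the Maintenance Treatment Period" (3.5.6). The AMS is "all participants who have received at least 1 dose (full or partial) of bimekizumab" (3.5.5).

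**The concern.** Two programmers following this text could produce different safety tables. One destination cannot be populated. Another puts events into a period whose time at risk stops earlier. The third works for bimekizumab participants but has no place for placebo participants who stopped before the Week 16 switch.

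TEAEs, serious TEAEs and TEAEs leading to withdrawal are the secondary safety endpoints (2.2.3.1). The tables built on these sets include serious TEAEs and TEAEs leading to death, with versions by relationship marked for regulatory reporting. A serious or fatal event that the SAP itself calls treatment-emergent could therefore be missing from the summaries for placebo.

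**Working it through.** **Inputs.** Initial Period cap of 112 days and the formula "Date of last dose in the Initial Treatment Period – Date of first dose in the Initial Treatment Period + 141" (10.1.1.2); TEAE window of last dose + 140 days (10.2.1); dosing every 2 weeks (section 7), so the last Initial Period dose falls on Day d = 1, 15, …, 99; 70 placebo participants (2.4).

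**The SAP's own figures.** 16 × 7 = 112 days and 20 × 7 = 140 days. Both reproduce.

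**Time at risk against the TEAE window.** With the first dose on Day 1, the dose-based term is d − 1 + 141 = d + 140. The window also ends on Day d + 140, which is d + 28 days past Day 112.

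| Last dose | d + 140 | Initial Period cap | Window past Day 112 |
|---|---|---|---|
| Day 1 | 141 | 112 | 29 days |
| Day 57 (Week 8) | 197 | 112 | 85 days |
| Day 99 (Week 14) | 239 | 112 | 127 days |

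The dose-based term is never below 141, so it never sets the minimum. Initial Period time at risk for this group never exceeds 112 days, and is less if last clinical contact or death comes first.

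**Each rule traced to its table.**

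1. *10.1.1.2, Maintenance summaries.* A participant who stopped in the Initial Period has no Maintenance dose and so is not in the MS. The event cannot be tabulated there.
2. *10.2.1, follow-up sentence.* The event would count in the Initial Period. This contradicts the exclusion in 10.1.1.2 and 10.2.2 and the Week 16 start-date rule in 10.2.1 itself. The exposure-adjusted event rate (EAER) divides by total time at risk, so it would count events whose time lies beyond the cap. The exposure-adjusted incidence rate (EAIR) runs exposure to the first event, so a participant with a first event after Day 112 would contribute more than 112 days while an event-free participant stays capped at 112.
3. *10.2.2, combined summaries.* Bimekizumab participants are in the AMS, and combined time at risk in 10.1.3.2 has no 112-day cap, so events and time match. Placebo participants receive bimekizumab only from Week 16 (2.3.2.2). One who stopped earlier is in neither the AMS nor the MS, and the Initial Period tables exclude the event. No TEAE summary table is left.

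**Size of the placebo gap.** Subject-years = n × (d + 28) / 365.25. The early-stopping rate is an assumption.

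- 10% of 70 = 7 people, last dose at Week 8: 7 × 85 / 365.25 = 1.6.
- Low end, 5% (3.5 people), Day 1 only: 3.5 × 29 / 365.25 = 0.3.
- High end, 15% (10.5 people), last dose Day 99: 10.5 × 127 / 365.25 = 3.7.

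These are upper limits for each scenario, because they assume follow-up to the end of the window.

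**The case against.** The strongest reply is that this is mostly a drafting slip. Sections 10.1.1.2 and 10.2.2 agree on the step that matters for the controlled comparison: events after Day 112 stay out of Initial Period output, which matches the 112-day cap. The follow-up sentence is general and the other two are specific, so a programmer would normally let the specific text govern. Section 10.2.2 then works for every bimekizumab participant. Much of this stands. It does not make the Maintenance destination executable, and it does not give late placebo events a table.

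Several stronger readings are tempting, and the SAP does not support them.

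- *The comparison with placebo is distorted.* The risk-difference tables are Initial Period tables (10.2.2, 10.2.3), and the exclusion applies to every arm alike.
- *Initial Period EAIRs carry events with no exposure.* EAIR exposure runs to the first event (10.2.1). The clean mismatch concerns the EAER, and only if the follow-up sentence overrides the two exclusions.
- *The events vanish.* Section 3.1 requires listings of all documented data. What is missing is a summary table.
- *The loss extends to all arms.* Applying 10% to all 490 participants gives 49 × 85 / 365.25 = 11.4 subject-years, but under 10.2.2 the bimekizumab events and time are retained. Only the placebo share is lost.

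A placebo participant given bimekizumab in error would enter the AMS; that is a narrow exception.

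**Conclusion.** The inconsistency is real in the current text. The Maintenance destination in 10.1.1.2 cannot be carried out, the follow-up sentence in 10.2.1 contradicts both exclusions, and under 10.2.2 late TEAEs of never-bimekizumab placebo participants reach no TEAE summary table.

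The amount of data is small: about 7 people and up to about 1.6 subject-years at an assumed 10% stopping with last dose at Week 8, and roughly 0.3 to 3.7 subject-years across the assumed 5% to 15% range. No efficacy result is touched, and the Initial Period safety comparison is unaffected if the exclusions are followed. The harm is incomplete placebo reporting and an allocation rule that can be programmed in more than one way. It should be corrected because the omitted events may be serious or fatal.

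**What to change.** 1. In 10.1.1.2, change the destination of these events from the Maintenance summaries to the combined Initial and Maintenance summaries, matching 10.2.2.
2. In 10.2.1, add an exception to the follow-up sentence: for participants never dosed in Maintenance, TEAEs after Day 112 are excluded from Initial Period tables, as in 10.2.2.
3. Keep the AMS for the combined tables. Add a separate placebo-only summary of Safety Set participants who never received bimekizumab, covering all TEAEs through last dose + 140 days, with time at risk per 10.1.3.2. It should include at least the overview, serious TEAEs, TEAEs leading to discontinuation and TEAEs leading to death.

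Moving the whole combined table to the Safety Set by randomised initial treatment is not needed. It would leave open how participants who switch from placebo to bimekizumab are handled.

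Cost: SAP wording and a few small extra tables. No additional data are required.

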10.1.2 Exposure during the Maintenance Treatment Period

Definitions for study medication duration (days) and time at risk (days) during the Maintenance Treatment Period are provided as follows:

10.1.2.1 Study medication duration (days)

Definitions for study medication duration (days) are provided as follows:

- Date of last dose in the Maintenance Treatment Period – date of first dose in the Maintenance Treatment Period + 14 days.

The use of 14 days assumes a Q2W dosing interval. For participants randomized to bimekizumab 320mg Q4W in the Maintenance Treatment Period, this will be adjusted based on the dosing interval (eg, use Date of last bimekizumab dose in the Maintenance Treatment Period – date of first dose in the Maintenance Treatment Period + 28 days).

Note: If date of last dose in the Maintenance Treatment Period + 14 days (or + 28 days in the case of Q4W dosing) extends to a date beyond the final visit date of the Maintenance Treatment Period (not including SFU), then this calculation reverts to:

- Final visit date of the Maintenance Treatment Period (not including SFU) – date of first dose in the Maintenance Treatment Period + 1.
- For participants who die during the Maintenance Treatment Period, then this calculation reverts to:
 - Date of death – Date of first dose in the Maintenance Treatment Period + 1.

10.1.2.2 Time at risk (days)

Definitions for time at risk (days) are provided as follows:

- For participants who complete the Maintenance Treatment Period as planned and continue into an extension study (and, therefore, do not have the SFU visit in the feeder study):
 - Date of last visit of the Maintenance Treatment Period – Date of first dose in the Maintenance Treatment Period + 1.
- For participants who die prior to the final visit of the Maintenance Treatment Period:
 - Date of death – Date of first dose in the Maintenance Treatment Period + 1.
- For all other participants, use the minimum of the following:
 - Date of last dose in the Maintenance Treatment Period – Date of first dose in the Maintenance Treatment Period + 141 days.

- Date of last clinical contact – Date of first dose in the Maintenance Treatment Period + 1.

Note: This group could include participants who discontinue the Maintenance Treatment Period early, participants who complete the Maintenance Treatment Period as scheduled but choose not to continue into an extension study, or participants who are ongoing in the SFU period at the time of the data snapshot.

10.1.3 Exposure during the Initial and Maintenance Treatment Period

Definitions for study medication duration (days) and time at risk (days) during the Initial and the Maintenance Treatment Period are provided as follows:

10.1.3.1 Study medication duration (days)

Definitions for study medication duration (days) are provided as follows:

- Sum of study medication durations from the individual Initial and Maintenance Treatment Period.

Note: The algorithms for calculating these durations are specified in Section 10.1.1.1 and Section 10.1.2.1.

Note: If date of last dose in the Initial Treatment Period + 14 days (or + 28 days in the case of Q4W dosing) extends to a date beyond the date of first dose in the Maintenance Treatment Period, then this calculation reverts to:

- Sum of study medication durations from the individual Initial and Maintenance Treatment Periods - 1.

10.1.3.2 Time at risk (days)

Definitions for time at risk (days) are provided as follows:

- For participants who complete the Maintenance Treatment Period as planned and continue into an extension study (and, therefore, do not have the SFU visit in the feeder study):
 - Final visit date – Date of first dose + 1.
- For participants who die prior to the final visit:
 - Date of death – Date of first dose in the + 1.
- For all other participants, use the minimum of the following:
 - Date of last dose – Date of first dose + 141 days.
 - Date of last clinical contact – Date of first dose + 1.

Note: This group could include participants who discontinue early, participants who complete the Maintenance Treatment Period as scheduled but choose not to continue into an extension study, or participants who are ongoing in the SFU period at the time of the data snapshot (in the case of the interim analysis).

10.2 Adverse events

An AE is any untoward medical occurrence in a patient or clinical study participant, temporally associated with the use of IMP, whether or not considered related to the IMP. An AE can therefore be any unfavorable and unintended sign (including an abnormal laboratory finding), symptom, or disease (new or exacerbated) temporally associated with the use of IMP.

10.2.1 Data considerations

Treatment-emergent AEs are defined as those AEs that have a start date on or following the first dose of study treatment through the final dose of study treatment + 140 days (covering the 20-week SFU period). If it is not possible (due to partial dates) to determine whether or not an AE is treatment-emergent then it will be assumed to be a TEAE.

An AE will be assigned to the Initial Treatment Period if it started between the first administration of IMP on Day 1 up to Week 16. An AE will be assigned to the Maintenance Treatment Period if it started between the Week 16 study drug administration and Week 48.

If an AE occurs on the date of a treatment switch, the event is attributed to the original treatment. The only exception to this is if the AE fulfills any of the criteria specified below:

- Events that fulfill the anaphylaxis criteria for acute events (refer to Appendix A in Section 12.1)
- Hypersensitivity events identified by the SMQ “Hypersensitivity (SMQ)” (see Section 12.1 Appendix A)
- Events with an high level term (HLT) of “Administration site reactions NEC”
- Events with an HLT of “Injection site reactions”

The rules for imputing partial start or stop dates are outlined in Section 4.2.4.

Any TEAEs that occur during the SFU Period will be attributed to the period in which the participant was before initiating the SFU Period.

Duration of AEs will not be calculated if there is missing stop date information.

If the intensity of an AE is unknown, it is considered as severe. If the relationship to study drug is missing, it is considered as related. Note that if the seriousness of an adverse event is unknown, every attempt should be made to resolve this prior to a snapshot for an interim analysis or database lock; in the exceptional case that the seriousness of an adverse event is still missing then no imputation should be applied for this characteristic.

Adverse events will be presented as “number of participants (percentage of participants) [number of events]”. In this style of output, “[number of events]” will include all cases of an AE including repeat occurrences in individual participants, while “number of participants” will count each participant only once.

Subject time at risk represents the time a participant is at risk for having an AE. The definitions for subject time at risk (in days) are outlined in Section 10.1. These definitions will be used for exposure-adjusted AE summaries.

Selected AE summaries will include the exposure-adjusted incident rate (EAIR) with associated 95% CI and the exposure adjusted event rate (EAER).

The EAIR is defined as the number of participants (n) with a specific AE adjusted for the exposure and will be scaled to 100 subject-years:

$$EAIR = 100 \times n / \sum_{i=1}^N (T_{Exp(i)})$$

Where $T_{Exp(i)}$ is the exposure time and N is the number of participants at risk.

If a participant has multiple events, the time of exposure is calculated to the first occurrence of the AE being considered. If a participant has no events, the total time at risk is used.

Exact Poisson 95% confidence intervals for incidence rates are calculated using the relationship between the Poisson and the Chi-square distribution (Ulm, 1990; Fay and Feuer, 1997):

$$LCL = \chi^2_{2n,\alpha/2} / 2$$

$$UCL = \chi^2_{2(n+1),1-\alpha/2} / 2$$

where n is the number of participants with a specific AE for the incidence rate of interest and is the basis for the number of the degrees of freedom for the chi-square quantile for the upper tail probability χ^2 .

The EAER will be the number of AEs including repeat occurrences in individual participants divided by the total time at risk scaled to 100 patient-years and calculated using:

$$EAER = 100 \times N_{AE} / \sum_{i=1}^N (T_{Risk(i)})$$

where N_{AE} is the total number of AEs, T_{Risk} is the time at risk for each participant, and N is the total number of participants at risk.

No confidence interval will be computed for EAER.

Selected summaries, as specified in Section 10.2.2, will include the risk difference between bimekizumab and placebo. The risk difference is calculated as:

$$RD = IP_{BKZ} - IP_{PBO}$$

where IP_{BKZ} is the incidence proportion for the bimekizumab-treated group and IP_{PBO} is the incidence proportion for the placebo group. Note that incidence proportion simply refers to the percentage of participants within the specified treatment group that experienced a given adverse event.

The standard error for the risk difference is calculated as follows:

$$SE_{RD} = \sqrt{\left(IP_{BKZ} \times \left(\frac{1 - IP_{BKZ}}{n_{BKZ}} \right) \right) + \left(IP_{PBO} \times \left(\frac{1 - IP_{PBO}}{n_{PBO}} \right) \right)}$$

where n_{BKZ} is the number of participants in the bimekizumab-treated group and n_{PBO} is the number of participants in the placebo group.

The corresponding confidence interval for the risk difference is as follows:

$$CI_{RD} = RD \pm Z_{1-\alpha/2} \times (SE_{RD})$$

where $Z_{1-\alpha/2}$ is the Z statistic for the corresponding level of alpha. For the risk difference confidence intervals calculated in this SAP, 1.96 will be used (corresponding to a two-sided alpha of 0.05 and 95% confidence interval). The risk difference and corresponding CI will be displayed as percentage.

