Suspected and confirmed COVID-19 cases will be identified with the preferred terms “Corona virus infection” or “Corona virus test positive”.

The following subset of tables will also be presented for the Maintenance Treatment Period using the MS:

- Incidence of TEAEs – Overview
- Incidence of TEAEs per 100 subject years by SOC, HLT, and PT
- Incidence of Serious TEAEs per 100 subject years by SOC, HLT, and PT
- Incidence of TEAEs Leading to Discontinuation per 100 subject years by SOC, HLT, and PT
- Incidence of TEAEs Leading to Death by SOC, HLT, and PT

The following tables will be presented for the Initial Treatment Period:

- Incidence of TEAEs Above Reporting Threshold of 5% with Risk Differences by SOC and PT
- Incidence of Serious TEAEs and Risk Differences by SOC and PT

The following table will be presented for the combined Initial and Maintenance Treatment Period. This summary will include only AEs that occur while a participant is on bimekizumab.

Any AEs in the Initial Treatment Period that begin while a participant is on placebo will be excluded.

- Incidence of TEAEs per 100 subject years by SOC, HLT, and PT and by Time of Onset Relative to Anti-bimekizumab Antibody Status. This will include columns for the following:
 - TEAEs starting before the first ADAb positive result (includes ADAb categories 2 and 5) where TEAEs have occurred before the following events: a) the first positive ADAb result for subjects in category 2 and b) the first post-Baseline boosted ADAb titer result for subjects with titer results and the first post-Baseline positive ADAb result for subjects with positive ADAb at Baseline with no other samples with titer available for subjects in category 5
 - TEAEs starting on the same date or after the first ADAb positive result (includes ADAb Categories 2, 3, 4, 5 and 6) where TEAEs have occurred on or after the following events: a) the first positive ADAb results for subjects in categories 2, 3, 4 and 6, and b) the first post-Baseline boosted ADAb titer result for subjects with titer results and the first post-Baseline positive ADAb result for subjects with positive ADAb at Baseline with no other samples with titer available for subjects in category 5
 - TEAEs for subjects who are ADAb negative at all timepoints (includes ADAb Category 1)

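### The exact Poisson limits printed for the EAIR in SAP 10.2.1 are limits for a count, not for a rate per 100 subject-years; the Wald risk-difference interval beside them is a correct formula but a weak choice for sparse events

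*SAP*

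**What the plan says.** SAP Section 10.2.1 defines the EAIR as 100 n / sum T_Exp, where n is the number of participants with the event, and states that it "will be scaled to 100 subject-years". For the interval it says "Exact Poisson 95% confidence intervals for incidence rates are calculated using the relationship between the Poisson and the Chi-square distribution" and prints two limits:

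- lower: "LCL = \chi^2_{2n,\alpha/2} / 2"
- upper: "UCL = \chi^2_{2(n+1),1-\alpha/2} / 2"

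It adds that n is the "basis for the number of the degrees of freedom for the chi-square quantile for the upper tail probability". No other section rescales these limits. Section 10.2.2 attaches the EAIR and its 95% interval to every TEAE summary expressed per 100 subject-years.

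For the risk difference, Section 10.2.1 gives the unpooled standard error and RD ± z × SE: "For the risk difference confidence intervals calculated in this SAP, 1.96 will be used". No alternative is given for sparse cells. Section 10.2.2 applies risk differences in the Initial Treatment Period to TEAEs above a 5% reporting threshold and, with no threshold, to "Incidence of Serious TEAEs and Risk Differences by SOC and PT". Section 10.2.3 applies them to each safety topic of interest.

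**The concern.** An interval for a rate must carry the same exposure and scale factor as the rate. The printed limits depend on n alone, so the same n gives the same interval in an arm of 280 and an arm of 70, although the rates differ fourfold. If programmed literally, every EAIR interval would be wrong unless the summed exposure happened to be 100 subject-years. The size of the error would also differ by arm, which distorts reading across columns.

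The tail wording is a second slip in the same place. If the subscripts are taken as upper-tail probabilities, the lower limit exceeds the upper.

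A lesser question concerns the risk difference. When no placebo participant has the event, the placebo variance term is zero, and the interval takes no account of uncertainty in the smallest arm.

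**Working it through.** **Inputs.** Group sizes for the Initial Treatment Period are pooled Q2W 280, Q4W 140 and placebo 70 (SAP Table 2-1). The period is 112 days (10.1.1.2) and years are days/365.25 (10.1). Event counts, and full exposure for everyone, are assumptions; the SAP gives no worked example.

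**Reproducing the plan's constant.** 2(1 − Φ(1.96)) = 0.0500, so 1.96 is right for a two-sided 95% interval.

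**Exposure.** Placebo 70 × 112/365.25 = 21.46 subject-years; Q4W 140 × 112/365.25 = 42.93; pooled Q2W 280 × 112/365.25 = 85.86. The missing factor 100/sum T_Exp is therefore 4.66, 2.33 and 1.16.

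**EAIR limits.** As printed: χ²(lower-tail 0.025; 2n)/2 and χ²(lower-tail 0.975; 2(n+1))/2. Rescaled: the same values × 100/sum T_Exp.

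| Arm | n | EAIR | Limits as printed | Limits rescaled |
|---|---|---|---|---|
| Placebo | 2 | 9.32 | 0.24 to 7.22 | 1.13 to 33.66 |
| Placebo | 5 | 23.29 | 1.62 to 11.67 | 7.56 to 54.36 |
| Q4W | 5 | 11.65 | 1.62 to 11.67 | 3.78 to 27.18 |
| Q4W | 10 | 23.29 | 4.80 to 18.39 | 11.17 to 42.84 |
| Pooled Q2W | 5 | 5.82 | 1.62 to 11.67 | 1.89 to 13.59 |
| Pooled Q2W | 10 | 11.65 | 4.80 to 18.39 | 5.59 to 21.42 |

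On placebo the printed interval excludes its own estimate at each of n = 2, 5, 10 and 20. Over longer follow-up the error changes direction. An arm of 140 followed for 48 weeks has 140 × 336/365.25 = 128.79 subject-years, so n = 5 gives an EAIR of 3.88, printed limits 1.62 to 11.67 and correct limits 1.26 to 9.06.

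**Tail wording.** For n = 10, reading the subscripts as upper-tail probabilities gives a lower limit of 17.08 and an upper limit of 5.49. The subscripts work only as lower-tail probabilities.

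**Risk difference, 4/280 v 0/70.** RD = 1.43%. SE = √(0.01429 × 0.98571/280 + 0) = 0.709%, so the Wald interval is 0.04% to 2.82%. Newcombe gives −3.85% to 3.61% and Miettinen-Nurminen −3.80% to 3.62%. Yet 0/70 is compatible with a true rate up to 1 − 0.025^(1/70) = 5.1%. With 0/280 v 0/70, Wald gives (0, 0) and Newcombe −5.20% to 1.35%.

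**Coverage of nominal 95% intervals, equal true risks, exact binomial enumeration.**

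| True risk | P(0 of 70) | Wald 280 v 70 | Newcombe 280 v 70 | Wald 140 v 70 | Newcombe 140 v 70 |
|---|---|---|---|---|---|
| 0.5% | 70.4% | 96.2% | 98.5% | 99.6% | 99.7% |
| 1% | 49.5% | 84.7% | 97.5% | 97.2% | 99.0% |
| 2% | 24.3% | 80.0% | 96.7% | 91.8% | 97.7% |
| 3% | 11.9% | 87.4% | 96.7% | 91.2% | 97.0% |
| 5% | 2.8% | 91.8% | 95.8% | 93.0% | 96.3% |

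At 2% and 280 v 70, the misses come almost wholly from trials with an empty placebo cell and an interval entirely above zero (19.7% of all trials).

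**The case against.** On the Poisson limits, the best defence is that the intention is plain. The method is named, it is said to be for incidence rates, the EAIR is defined just above, and a competent programmer would rescale. That stands to this extent: the harm is conditional on literal programming, and the EAIR itself is correctly defined. It does not remove the error, because a SAP formula should be executable as written. Nor would a wrong interval always look wrong: on pooled Q2W the printed limits contain the estimate at every count tried from 0 to 20.

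The 4.7-fold figure applies to placebo only; for pooled Q2W the factor is about 1.2. Full exposure is an idealisation, because Section 10.2.1 stops the clock at the first occurrence. In these arms, shorter exposure makes the missing factor larger.

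On the risk difference, a reader might infer that this formula too is wrong, and that the interval collapses whenever placebo has no events. The SAP does not support that. The unpooled Wald standard error and the 1.96 are stated correctly. An empty placebo cell removes only the placebo term, and 4/280 v 0/70 keeps a non-zero width. Zero width arises when neither arm has an event (or everyone in both does). The choice of interval also leaves the point estimate, 1.43% in that example, unchanged, and the dot plots are ordered by that estimate. Undercoverage is not general either: Wald is above nominal at 0.5% in both comparisons, and the table limited to TEAEs above 5% is affected less.

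**Conclusion.** The EAIR limits in Section 10.2.1 are wrong as written and need correcting. They are on the count scale, and the tail description contradicts the subscripts. Under full 112-day exposure and planned arm sizes, limits for the Initial Treatment Period are too low by about 4.7-fold (placebo), 2.3-fold (Q4W) and 1.2-fold (pooled Q2W), so comparison between arms is distorted as well. The scale factors rest on those exposure assumptions; the event counts are illustrative.

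The Wald interval is a matter of method, not a mistake. Its undercoverage is real but concentrated at true risks of about 1% to 3% in the pooled Q2W comparison (84.7%, 80.0%, 87.4%). It is milder for Q4W at the same risks (97.2%, 91.8%, 91.2%). Score-type limits are a worthwhile improvement for the sparse tables.

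Neither part touches the Type I error control of Section 4.5, which covers the primary and secondary efficacy endpoints only.

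**What to change.** In Section 10.2.1, replace the EAIR limits with:

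- LCL = 100 × χ²(lower-tail 0.025; 2n) / (2 × sum T_Exp), with LCL = 0 when n = 0
- UCL = 100 × χ²(lower-tail 0.975; 2(n+1)) / (2 × sum T_Exp)

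Delete the upper-tail description, and state that T_Exp is in years. This costs a few lines of text.

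As a secondary change, specify Miettinen-Nurminen or Newcombe limits for the risk differences in the serious-TEAE and safety-topic tables and their plots. This is a SAS option in PROC FREQ. The price is somewhat wider intervals for rare events. Neither change affects data collection or design.
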